3.0 Objectives

3.1 Primary Objectives

- 3.1.1 To assess whether treatment with IMPT results in longer time to cognitive failure compared with IMRT. Cognitive failure is defined as the first cognitive failure on any of the following six cognitive outcome variables: Hopkins Verbal Learning Test Revised (HVLT-R) Total Recall, HVLT-R Delayed Recall, HVLT-R Delayed Recognition, Controlled Oral Word Association (COWA), Trail Making Test (TMT) Part A or Part B.
- 3.2 Secondary Objectives
 - 3.2.1 To determine local control in the brain post radiation treatment.
 - 3.2.2 To determine overall survival in each treatment arm.
 - 3.2.3 To assess quality of life measured at two month intervals for a total of two years post-radiotherapy for both treatment arms.
 - 3.2.4 To assess the pattern of cognitive change in memory at two month intervals for two years post-treatment as well as executive function and processing speed.
 - 3.2.5 MRI diffusion weighted images (DWI) and reconstructed apparent diffusion coefficient (ADC) maps will be analyzed to see if there is a difference between pre- and post-treatment scans. These will also be analyzed for differences between the two treatment modalities.
 - 3.2.6 To evaluate if diffusion tensor imaging (DTI) correlates to the cognitive changes and if there are differences between the two treatment modalities.
 - 3.2.7 To assess the pre-treatment factors of recursive partitioning analysis (RPA) class and mini mental status examination (MMSE) in the predictive determination of local and distant control and cognitive outcome in each treatment arm.
 - 3.2.8 To assess the correlation between location of primary lesion, total volume of intracranial disease, and cognitive outcome in each treatment arm.
 - 3.2.9 To determine the relationship between MGMT promoter methylation status and cognitive and local control outcomes.
 - 3.2.10 To document and descriptively compare post-treatment adverse side effects between the two treatment arms.
 - 3.2.11 To determine the relation between dosimetric parameters and cognitive and local control outcomes.
- 3.3 Correlative objectives
 - 3.3.1 To determine if Apo E (i.e., Apo E2, Apo E3, and Apo E4) genotyping may prove to be a predictor of radiation induced neurocognitive decline (or neuro-protection).
 - 3.3.2 To determine if inflammatory markers (i.e., IL-1, IL-6, and TNF- α) may prove to be predictors of radiation induced neurocognitive decline.

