10.0 Criteria for Response and Toxicity

10.1 Definition of primary endpoint:

- 10.1.1 Time to cognitive failure on any of the 6 primary variables from the pre-specified cognitive tests (HVLT-R total recall, HVLT-R delayed recall, HVLT-R delayed recognition, TMT Part A or Part B, COWA) with failure defined as a decline that meets or exceeds the reliable change index (RCI) for each cognitive test variable. A cumulative incidence approach will be used to estimate median time to cognitive failure in order to account for the competing risks of disease progression and death. Patients experiencing disease progression or patients that died prior to experiencing cognitive failure will be considered as having had a competing event. Progressive disease frequently causes cognitive decline, and the goal of this study is to assess the impact of the radiation treatment itself on cognitive decline.
- 10.2 Definitions of secondary endpoints:
 - 10.2.1 Local control and distant control in the brain will be measured by contrast-enhanced brain MRI scan using Response Assessment in Neuro-Oncology (RANO)Criteria, as follows [50].
 - 10.2.1.1 Complete Response (CR): Requires all of the following 1) complete disappearance of all enhancing measurable and non-measurable disease sustained for a minimum of 4 weeks; 2) no new lesions; 3) stable or improving nonenhancing (T2/FLAIR) lesions; 4) patients must be off corticosteroids (or on physiologic replacement doses only); and 5) stable or improved clinically.
 - 10.2.1.2 Partial Response (PR): Requires all of the following: 1) ≥50% decrease compared with baseline in the sum of products of perpendicular diameters of all measurable enhancing lesions sustained for at least 4 weeks; 2) no progression of non-measurable disease; 3) no new lesions; 4) stable or improved non-enhancing (T2/FLAIR) lesions on the same

or lower dose of corticosteroids compared with the baseline scan; 5) stable or improved clinically.

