10.2.1.3 Progressive Disease (PD): Defined as any of the following 1) \geq 25% increase in the sum of the products of perpendicular diameters of enhancing lesions compared with the smallest tumor measurement obtained either at baseline (if no decrease) or best response, on stable or increasing dose of corticosteroids; 2) significant increase in T2/FLAIR nonenhancing lesion on stable or increasing doses of corticosteroids compared with baseline or best response not caused by comorbid events (i.e. radiation therapy. demvelination, ischemic injury postoperative changes); 3) any new lesion; 4) clear clinical deterioration not attributable to other causes apart from tumor (i.e. seizures, medication adverse effects, complications of therapy, cerebrovascular events, infection, or decrease in corticosteroid dose); 5) failure to return for evaluation due to death or deteriorating condition; 6) clear progression of non-measurable disease.

When making the diagnosis of progressive disease it is import to recognize the possibility of pseudo-progression, especially if the patient is clinically stable. In those situations, treatment should continue and status of local control should be evaluated with a repeat interval scan. If the subsequent scan confirms progression then the date of progression should be backdated to the original scan suggesting progression.

- 10.2.1.4 Stable Disease (SD): Requires all of the following 1) does not qualify for complete response, partial response, or progression; 2) stable FLAIR/T2 lesions on corticosteroid dose no greater than at baseline; 3) clinical status stable.
- 10.2.1.5 For local control, PD is considered local failure, or stable disease with deterioration of the neurological examination with a grade III or worse toxicity on the CTCAE v.4.0 scale (see Appendix). All others (CR, PR, asymptomatic SD) are deemed success.
- 10.2.2 Overall survival will be measured from registration until death. After 2 years of follow-up event monitoring will be used.
 - 10.2.2.1 Patients with unknown vital status will be censored at the date of last visit or MRI scan.
- 10.2.3 Quality of life will be measured at each two month interval follow up visit out to two years using the EORTC QLQ C30/BN20 and the MD Anderson Symptom Inventory Brain Tumor (MDASI-BT).

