- 10.2.4 At each two month interval follow up visit out to 2 years all six prespecified cognitive test variables will be assessed. The pattern of cognitive change in memory, executive function, and processing speed will be assessed at each time point. The composite cognitive function

score will be determined by averaging standardized Z-scores from all pre-specified cognitive test variables (5 out of 6 are required to calculate a composite score).

- 10.2.5 MRI imaging including diffusion weighted images (DWI) and reconstructed apparent diffusion coefficient (ADC) maps will be analyzed for differences between pre- and post-treatment scans. They will also be analyzed for differences between the two treatment modalities.
- 10.2.6 Diffusion tensor imaging (DTI) will be analyzed for correlation to the cognitive changes and for differences between the two treatment modalities.
- 10.2.7 Pre-treatment factors of RPA class and MMSE will be assessed for predictive determination of local and distant control and cognitive outcome in each treatment arm.
- 10.2.8 Assessment will be made for correlation between location of primary lesion, total volume of intracranial disease, and cognitive outcome for each of the treatment arms.
- 10.2.9 The relationship between MGMT promoter methylation status and cognitive and local control outcomes will be assessed.
- 10.2.10 Post treatment side effects will be recorded at each follow up visit out to two years. Toxicity will be recorded according the Common Terminology Criteria for Adverse Events v4.0.3 for Nervous System Disorders. Only grade 3 and above toxicity that is directly related to therapy will be required to be documented. Pretreatment symptoms should not be considered as toxicity related to the treatment and are not required to be documented unless the symptoms worsen as a result of therapy.
- 10.2.11 Dosimetric parameters such as dose to the hippocampus will be analyzed for relationship with cognitive and local control outcomes.
- 10.3 Evaluation of correlative markers
 - 10.3.1 Genetic markers: DNA will be extracted within the first five fractions of treatment in the laboratory of the Study Chair. Apo E (i.e., Apo E2, Apo E3, and Apo E4) genes will be analyzed for single nucleotide polymorphisms (SNPs) either by Taqman or direct sequencing.

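### Local failure has no location limit and takes in some deaths, while distant failure is analysed but never defined

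*Combined protocol and SAP*

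**What the plan says.** Section 10.2.1 names two outcomes, "Local control and distant control in the brain will be measured by contrast-enhanced brain MRI scan", both assessed with the RANO categories. Section 10.2.1.3 lists six criteria for PD, any one of which is enough. Item 3 is "any new lesion", with no site attached. Item 5 is "failure to return for evaluation due to death or deteriorating condition".

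Section 10.2.1.5 then sets the endpoint: "For local control, PD is considered local failure". It adds a second route to failure through stable disease, which is not at issue here, and closes with "All others (CR, PR, asymptomatic SD) are deemed success".

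Distant control appears as an outcome in its own right elsewhere. Objective 3.2.7 asks for "predictive determination of local and distant control and cognitive outcome in each treatment arm", and 10.2.7 repeats the aim.

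Section 12.4 estimates the cumulative incidence of local failure and fits a Fine and Gray model to compare the arms, with death as the competing event in both. It says that time to distant failure will be analysed in the same way. No section says what a distant failure is, or where local ends and distant begins.

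**The concern.** A between-arm analysis of local failure needs to know which recurrences are local, and which patients leave the local-failure process by dying. The endpoint text answers the first question by counting all PD. On the second it disagrees with the analysis section. The distant-failure analysis has no defined event.

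The planned uses of these outcomes are more than descriptive. Local control is the first secondary objective (3.2.1). Local control, or local and distant control together, is also the outcome for RPA class and MMSE (3.2.7, 10.2.7), MGMT status (3.2.9, 10.2.9) and dosimetric parameters (3.2.11, 10.2.11). Section 12.4 puts selected dosimetric parameters into the local-failure model. If remote recurrences and some deaths sit among the events, those models no longer describe control at the treated site.

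**Working it through.** The plan gives no sample size, power or expected rate for local or distant control, so there is no stated figure to reproduce. The check is a reading of the sections side by side.

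**Step 1: can a patient with a remote-only new lesion be a local success?** Success requires CR, PR or asymptomatic SD. CR and PR each require that there be no new lesions (10.2.1.1, 10.2.1.2). SD requires that the patient not qualify for progression (10.2.1.4). A new lesion at any site is PD under item 3. None of the success categories is open, so the patient is a local failure.

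**Step 2: how is each type of patient coded?**

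| Patient | 10.2.1.3 with 10.2.1.5 | 12.4 |
|---|---|---|
| Progression at the treated site | Local failure | Local failure |
| New lesion at a remote site only | Local failure (item 3) | Distant failure is to be analysed, but is not defined |
| Death, no earlier PD, evaluation still due | Local failure (item 5) | Competing event |
| Death after documented PD | Already a local failure | No conflict: the event came first |
| Death, no earlier PD, after scheduled evaluations end | Item 5 not met | Competing event, no conflict |

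Evaluations are due for 24 months after treatment (9.1). Only the second and third rows are in difficulty.

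**Step 3: the primary endpoint.** Sections 10.1.1 and 12.3 treat progression and death before cognitive failure alike, as competing events. Neither the site of a progression nor the choice between calling a death PD or death changes which patients have a cognitive failure.

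**Step 4: illustration of size.** Inputs: target enrolment 90 (12.2) and equal allocation (7.1), so 90/2 = 45 per arm. This takes the planned enrolment as the denominator. If d deaths in an arm change from competing event to local failure, the crude local-failure proportion in that arm rises by d/45:

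- d = 1: 1/45 = 2.2 points
- d = 3: 3/45 = 6.7 points
- d = 5: 5/45 = 11.1 points

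The documents do not give d; the three values are assumptions that show the scale only.

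A remote-only first PD behaves differently. Under a location rule it leaves the local-failure count only if no local failure is seen later. If one follows, the count stays the same and only the event date moves. Because routine MRI runs until recurrence (9.3), a later local failure may go unobserved, so the plan also has to say how such patients are handled.

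**The case against.** The strongest reply is that 10.2.1.5 opens by limiting itself to local control and sits under a section that names local and distant control separately, so PD there may be meant as PD at the treated site. That is a plausible intent. But no section says so or draws the boundary. Even on that reading, distant failure remains undefined and item 5 still conflicts with 12.4.

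On deaths the reply is better. Section 10.2.1 says that control is measured by MRI, suspected pseudo-progression is settled by a repeat scan, and 12.4 is the specific analysis rule. It is likely that death is meant to compete, and what stands is a conflict of wording that needs a short correction.

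Section 13.2 lets the study chairman settle differences of opinion. That resolves disputes; it is not a prespecified coding rule.

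A reader might also infer more than the documents support:

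- *That the comparison is biased toward one arm.* The same text applies to both arms, and nothing in the documents gives a direction.
- *That the number of miscoded patients can be calculated.* One could apply the cited historical 2-year survival of 27.2% (section 4.0) to the 60 evaluable patients. But 12.2 requires an evaluable patient to have completed a follow-up cognitive test, which removes those who die before it. The share of deaths without earlier PD is not given either.
- *That each remote-only recurrence shifts the local-failure proportion.* As shown above, it may shift only the date.

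**Conclusion.** The point holds. Applied as written, 10.2.1.5 counts remote-only recurrences, and deaths without earlier PD while evaluations are due, as local failures. The first sits badly with a separate distant outcome that has no definition; the second contradicts 12.4.

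The effect is confined to the secondary local and distant failure analyses, and the primary endpoint does not change. Its overall size cannot be derived, because the documents give neither the share of first progressions that are remote nor the share of deaths without earlier PD. The figure of about 2.2 points per recoded death rests on 45 patients per arm and refers to the crude proportion, not to the cumulative incidence that 12.4 will estimate. The correction should be made before these outcomes are analysed.

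**What to change.** In 10.2.1.5, prespecify a location rule. One example: local failure is PD on imaging within or contiguous with PTV-50 (the larger planning volume in 7.3), and distant failure is PD on imaging wholly outside it. Another boundary would serve equally well if fixed in advance. Classify from the MRIs and treatment plans already obtained.

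In the same place, state how three cases are coded:

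- a scan that shows progression at both sites;
- PD that is clinical only, without imaging;
- a first failure at the other site, given that routine MRI stops at recurrence.

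State that death without prior PD is a competing event only, as in 12.4, so that the death part of PD item 5 does not count as local failure. Keep overall RANO PD as the competing event in the primary endpoint.

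The cost is protocol and analysis-plan wording, plus a review of first-PD scans against the treatment plans, at most one per progressing patient. That review is an added step, because 9.3 describes comparison with baseline scans only. No new scans or visits are needed. There would be slightly fewer local-failure events.

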14.0 Reporting Requirements

14.1 Radiation using either photon or proton technique has known associated risks, including tumor swelling, neurological decline, edema, and radiation necrosis. Nonetheless, radiation is considered standard of care. Adverse treatment reactions will be reported to the IRB. Standard monitoring procedures as noted above to detect and treat postoperative complications will be followed.

- 14.2 All attempts will be made to preserve patients' confidentiality. Patient records will be kept electronically or in secure file cabinets and handled only by responsible personnel.
- 14.3 Study progress and analyses of safety data will be presented to the MDACC DSMB on an annual basis, or as requested.

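### The local-failure rule in 10.2.1.5 counts grade III or worse neurological toxicity with stable disease whatever its cause, contradicts the SD and PD definitions beside it, and can shift the comparison between arms if toxicity differs

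*Combined protocol and SAP*

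**What the plan says.** Section 10.2.1 bases local and distant control on contrast-enhanced MRI read by RANO criteria. Section 10.2.1.5 then counts as local failure PD, "or stable disease with deterioration of the neurological examination with a grade III or worse toxicity on the CTCAE v.4.0 scale". It closes: "All others (CR, PR, asymptomatic SD) are deemed success".

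The neighbouring definitions (10.2.1.3 and 10.2.1.4) are:

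- **PD item 4** accepts "clear clinical deterioration not attributable to other causes apart from tumor". The other causes it lists are seizures and "medication adverse effects, complications of therapy, cerebrovascular events, infection, or decrease in corticosteroid dose".
- **PD item 2** leaves out T2/FLAIR change caused by radiation therapy, among other comorbid events.
- **SD item 3** requires the patient's clinical status to be stable. SD item 2 requires a corticosteroid dose no higher than at baseline.

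Toxicity has its own endpoint. Section 10.2.10 uses CTCAE v4.0.3 for nervous system disorders and states: "Only grade 3 and above toxicity that is directly related to therapy will be required to be documented". Objective 3.2.10 is "To document and descriptively compare post-treatment adverse side effects between the two treatment arms". Section 14.1 lists "neurological decline, edema, and radiation necrosis" among the known risks of radiation by either technique.

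Section 12.4 estimates local failure by the Gooley method and tests the arms with a Fine-Gray model, with death as the competing event and selected dosimetric parameters as covariates. Objective 3.2.11 is "To determine the relation between dosimetric parameters and cognitive and local control outcomes". Section 12.4 plans analyses of all patients and of evaluable patients, and as-treated versions of nearly all of them, but no analysis of local failure restricted to PD.

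**The concern.** Local control should tell the reader whether the tumour was held. The added clause lets a patient whose tumour has not progressed count as a local failure because of a severe neurological event, and it does not ask what caused that event. A radiation injury with a stable scan could then appear twice: as toxicity under 10.2.10 and as lost tumour control under 10.2.1.5.

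This matters more here than in most trials, because the arms were chosen for an expected difference in dose to normal brain (sections 4.0 and 5.1). An endpoint that contains toxicity is exposed to the effect under study. A difference in side effects could be read as a difference in tumour control, in either direction. In the dosimetric analysis, a higher dose to normal brain could appear related to local failure through toxicity alone.

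**Working it through.** **1. The definitions side by side.** Take a patient with a stable scan and a grade III neurological deterioration attributed to treatment.

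| Rule | Result |
|---|---|
| PD item 4 | Not PD: complications of therapy are left out |
| SD item 3 (10.2.1.4) | Not SD: clinical status is not stable |
| CR, PR (10.2.1.1, 10.2.1.2) | Neither: both require the patient to be clinically stable or improved |
| 10.2.1.5, added clause | Local failure, if SD is read as a stable scan |
| 10.2.1.5, success list | Not a success: the SD is not asymptomatic |
| 10.2.10 | Recorded as therapy-related toxicity |

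Read literally, SD item 3 leaves the clause with almost no patients. But 10.2.1.5 names the group and restricts success to asymptomatic SD, so the clause was evidently meant to operate. The two sections cannot both stand as written.

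**2. Possible size.** The plan states no rate or design figure for local control, so there is none to reproduce. All inputs here are assumptions:

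- PD hazard equal in both arms, with median 7 or 9 months: λ = ln 2/7 = 0.0990 or ln 2/9 = 0.0770 per month.
- Toxicity counted by the clause, as 12-month risk p in the absence of PD: τ = −ln(1−p)/12 per month. This gives 0.00168 (2%), 0.00254 (3%), 0.00427 (5%), 0.00878 (10%) and 0.01354 (15%).
- Exponential times; death ignored.

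Apparent HR (IMPT/IMRT) = (λ + τ for IMPT)/(λ + τ for IMRT). The true HR for tumour control is 1.00 throughout.

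| 12-month toxicity, IMRT vs IMPT | HR, median 7 | HR, median 9 |
|---|---|---|
| 5% vs 2% | 0.975 | 0.968 |
| 10% vs 3% | 0.942 | 0.927 |
| 15% vs 5% | 0.918 | 0.898 |

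Example (median 9, 15% vs 5%): (0.07702 + 0.00427)/(0.07702 + 0.01354) = 0.08129/0.09056 = 0.898. Six-month local failure is 1 − exp(−6 × 0.09056) = 41.9% with IMRT and 1 − exp(−6 × 0.08129) = 38.6% with IMPT. The PD-only value is 1 − exp(−6 × 0.07702) = 37.0% in both.

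**3. Equal toxicity.** With 10% in both arms and a 9-month median, the HR is 1.00, but six-month failure is 1 − exp(−6 × (0.07702 + 0.00878)) = 40.2% in each arm instead of 37.0%. That is overcounting without bias between arms.

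**4. Higher toxicity.** With an assumed 12-month PD risk of 50% and toxicity of 20% vs 5%, 12-month failure is 1 − 0.50 × 0.80 = 60.0% vs 1 − 0.50 × 0.95 = 52.5%. The HR is ln(0.50 × 0.95)/ln(0.50 × 0.80) = 0.81. The size depends almost wholly on the assumed rates.

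**5. Size against noise.** With an assumed 80 local-failure events, SE(log HR) ≈ 2/√80 = 0.22. An HR of 0.898 is |ln 0.898|/0.22 = 0.108/0.22, about half a standard error.

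**The case against.** The clause may be a deliberate, conservative choice. PD item 4 requires clear deterioration with other causes set aside, so tumour-driven decline of uncertain cause could escape it, and the clause catches those patients. It also catches stroke, seizure and infection. The documents give no split by cause, so a reader who infers that the clause mainly adds radiation injury goes further than the text allows. This part of the objection stands.

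A reader might also infer that the comparison will favour IMPT. The documents do not support that. Bias needs unequal toxicity, and the plan states an expectation about dose to normal tissue, not a toxicity rate. If protons caused more injury, the bias would run the other way. If SD item 3 were applied literally, hardly anyone would enter through the clause and the bias would nearly vanish, leaving the contradiction.

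Nor is a PD-only rule free of radiation injury. PD item 1 (growth in enhancement) has no exclusion by cause, although 10.2.1.3 handles suspected pseudo-progression by a repeat scan. PD item 5 counts failure to return because of a deteriorating condition, again without a cause. The HR of 1.00 under a PD-only rule is built into the illustration and is not a finding.

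Finally, the clause refers to an Appendix that is not in the text supplied. The absence of a cause test is a statement about the visible text only.

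None of this removes the contradiction between 10.2.1.4 and 10.2.1.5, or the overlap with 10.2.10.

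**Conclusion.** The point holds in a limited form. The certain defect is definitional: 10.2.1.5 conflicts with SD item 3, and it can score as local failure the therapy-related deterioration that PD item 4 leaves out and 10.2.10 records separately. The bias between arms is conditional. It needs the clause to be applied to patients with a stable scan, and toxicity to differ by arm. Under the assumed rates of 5–15% vs 2–5% the apparent HR is 0.898 to 0.975, which is modest beside the sampling error of a trial enrolling 90 patients. These figures omit death, which the Fine-Gray model treats as competing, so they show scale only.

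The effect is confined to the secondary local-control endpoint and the analyses built on it: section 12.4, and objectives 3.2.7, 3.2.9 and 3.2.11 where they use local control. It would be wrong to infer that the primary result is compromised. The competing events there are disease progression and death (10.1.1 and 12.3), not local failure as 10.2.1.5 defines it. The correction is worth making because it is cheap and the endpoint is tested between arms.

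**What to change.** 1. In 10.2.1.5, for the local-control analysis, define local failure as RANO PD (10.2.1.3) only.
2. Replace the closing success list with wording under which every patient not meeting PD is locally controlled, and say expressly that this includes a stable scan with deterioration not attributed to tumour. Deleting the toxicity clause alone is not enough: such a patient would fit neither PD nor the remaining success list.
3. Reconcile this wording with item 3 of 10.2.1.4.
4. Report grade 3+ neurological toxicity under 3.2.10 and 10.2.10.
5. Keep the present composite, under its own name, as a sensitivity analysis in 12.4.

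The cost is a short protocol edit using data already collected. The price in the analysis is slightly fewer local-failure events and later scoring of some tumour-driven decline of uncertain cause. Radiation injury that meets PD item 1 or 5 can still count, and the report should say so.
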